5 OBJECTIVES AND ENDPOINTS

Table 2. Overview of Study Aims, Design, and Outcomes

	Study design and interventions	Outcomes
--	--------------------------------	----------

Aim 1	 Self-reported HIV testing within 3 months of intervention start BMU census / registry verification & updating Baseline social network data collection Identification of close social networks and network-central 'promoters' Baseline survey among those randomized to control and intervention RCT: Intervention: Promoters given training & multiple STs, & asked to offer STs to men in their social networks. Control: Promoters given basic training & vouchers for HIV testing (including HIVST) at clinics to offer to men in their networks 3-month follow-up survey Measure impact of intervention on linkage to & uptake of ART & PrEP Intervention: Promoters are given incentives (clinic transport reimbursement vouchers valued at ~\$5) & encouraged to give to men in their networks to promote linkage to ART or PrEP 	 Self-reported HIV testing uptake within 3 months Confirmatory HIV testing uptake 3 – 6 months after intervention start Linkage to ART or to PrEP within 3 months after self-reported HIV testing Initiation of ART or PrEP (among those eligible), within 3 months of confirmatory testing (linkage)
	 after HIV testing 2. Control: Promoters given same training & info, but no linkage incentives 	
Aim 3	 Measure impact of intervention on ART & PrEP retention & adherence Men who test HIV-positive undertake VL testing and counseling at scheduled intervals to ascertain adherence to ART Men who test HIV pagative 	 Viral suppression (HIV RNA <400 c/mL) and adherence at 6 & 12 months Adherence to PrEP (TFV levels of >=1500
	 Men who test HIV-negative undertake rapid HIV & TFV testing with counseling at scheduled intervals and urine testing to ascertain PrEP adherence 	ng/mL in urine = adequate adherence ²⁸) at 6 months
Qualitative	Across all aims, we will assess the path mixed methods quantitative and qualit	ways of intervention action using qualitative and ative assessment. We will identify the

Studies	mechanisms of action, and barriers and facilitators of the social network and incentives
	intervention implementation, using qualitative and mixed methods quantitative and
	qualitative assessments embedded in Aims 1, 2 and 3. The data collection approach will
	include in-depth interviews with participants in both groups, key informant interviews
	with network-central promoters, and focus group discussions with study participants
	stratified by HIV status and study group. Data will be collected at baseline and at follow-
	up periods corresponding to the timing of quantitative outcome measurements in Aims
	1 through 3.

6 STUDY DESIGN

6.1 OVERALL DESIGN

This study among fishermen at beach landing sites in Siaya County, Kenya, is a 5-year combination prevention study using both novel biomedical tools and low-cost behavioral interventions to pursue three outcomes corresponding to the study's aims: 1) to increase men's HIV testing with self-tests; 2) to improve care linkage to prevention or treatment among men who HIV test; and 3) to assess the long-term impacts of the intervention on men's engagement in HIV care and prevention, including adherence. The study includes qualitative and mixed methods- quantitative and qualitative assessments in all aims, designed to ascertain the pathways of intervention action and to identify key implementation factors that affect outcomes. The study design is a cluster randomized controlled trial where the unit of randomization will be a clusters of men's close social network in study communities. Prior to the study launch, we will conduct a pilot for the study which will test survey instruments and refine our approach for the main RCT. **PILOT SURVEY AND QUALITATIVE INTERVIEWS**

We will conduct a small pilot in a beach-landing site in order to refine and improve our study approach and data collection tools. The data collected from this pilot social network mapping will not be included in the main study. In order to conduct this pilot, we will, utilizing locally available data and information, select a beach community to conduct the activity. The consent forms, enrollment, and eligibility screening procedures, including incentives for participation, will outlined in the sections to follow.

NB: COVID amendment:

Implementing phone-based data collection. In response to COVID-19 related disruptions, and in an effort to avoid further delays, we may utilize phone-based data collection to collect key demographic and social network data during the pilot phase. In the event of COVID-19 related restrictions being lifted in June or July of 2020, we will resume our modified in-person data collection, adhering to local, IRB and country-level mandated guidelines for social distancing and human subjects' protections.

Should it become necessary to implement phone-based data collection during the pilot phase, we will screen and determine eligibility using the larger study criteria detailed in section 7.1, verbal recruitment script and versions of the screening form- one for phone and one for in-person. We will provide incentives of 500 KSH via *Mpesa*, for all those who participate in any potential phone survey for this pilot. If pilot data is collected in person, the incentive will be provided in-person. We will conduct the pilot survey (attached to the protocol) with eligible (18 and older, men who are involved in fishing or related

occupations), after screening (using the pilot phone-based *or* in-person screening form) and consenting them using (the pilot phone-based consent form-verbal *or* the written pilot consent form) - attached to this protocol. Once we have conducted these surveys, we will take the information obtained to map social networks. Based on the data obtained from the pilot survey, we will also purposively select up to n=20 men who will be invited for additional in-depth interviews. This rapid interview will utilize the instruments attached to this protocol (see qualitative pilot interview). Information obtained during this pilot phase, from both the surveys and subsequent qualitative interviews, will be utilized to modify, improve, and adjust the survey and study approach. Subsequent modifications will be submitted to IRB.

6.2 BEACH CENSUS/REGISTRY VERIFICATION & ABSTRACTION

Tool for the baseline BMU Census/Registry data verification, updating and abstraction is included as appendix to this protocol.

6.3 SOCIAL NETWORK SURVEY

We will contact fishermen identified during the BMU census/registry data abstraction to screen for eligibility in the study. Fishermen who provide informed consent will be administered a baseline survey that elicits information on the close social networks of fishermen. This module will ask participants to name the men in their community to whom they are most closely connected to for domains such as health (whom they would seek health information from or share information with), finances (to whom they would turn to borrow money), and spending time (on work and social activities). The social network data obtained in this way will enable us to determine the ties and close social networks that exist in the community, particularly among fishermen. The procedures for the baseline survey are described in detail in the study procedures section.

The social network survey instrument is included as an attachment to this protocol.

6.4 IDENTIFICATION OF CLOSE SOCIAL NETWORKS AND NETWORK-CENTRAL PROMOTERS

Using the social network data obtained from the baseline survey and BMU census/ registry data along with a name-matching algorithm, we will identify male close social networks that exist in study communities. Their defining characteristic will be that individual members of any given network will be connected to each other on multiple domains that indicate strong ties between them. Following the identification of distinct close social networks in communities, we will analyze the network data to determine a network-central individual having a high degree of connectedness across domains within each network. The network-central individual will be considered as the network-central 'promoter' of HIV testing and will be the main individual study staff will contact to implement intervention and control group activities and approached for consent. If a central individual is not interested in participation, we will approach the next most central individual. Local close networks with consenting promoters will be eligible for randomization.

6.5 RANDOMIZATION OF CLOSE SOCIAL NETWORKS

Close social networks will be randomized 1:1 to intervention and control arms using a computer algorithm

that performs randomization stratified by beach and network size in blocks of two networks. All network members will receive the study arm condition to which their network is assigned. Participation of all network members is not a requirement for network randomization.

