3 PROTOCOL SUMMARY

3.1 SYNOPSIS

Title:	Self-Test Strategies and Linkage Incentives to Improve ART and PrEP Uptake in Men			
Grant Number:	1R01 MH120176			
Brief Summary:	This is a randomized controlled trial to test a combination behavioral and biomedical intervention to improve the HIV prevention and care cascades in a population of mobile men in a high priority setting (fishermen in Kenya). The intervention strategy is to recruit and train highly socially-connected men to distribute HIV self-tests and provide linkage support to men in their close social networks. The study will determine whether this social network-based approach along with small financial incentives in the form of transport vouchers and biomedical technologies can increase men's HIV testing (within3 months linkage to and uptake of ART and PrEP after testing (within 3 months, and virologic suppression (HIV RNA < 400 c/mL) at 6 months and PrEP adherence (tenofovir levels of >=1500 ng/mL in urine) at 6 months. The study includes a longitudinal qualitative and mixed methods quantitative and qualitative assessments to identify the pathways of intervention action, and understand how the social network-based approach with support for linkage affects testing and ART and PrEP uptake and retention in men.			
Study Design:	Cluster randomized controlled trial of a combination intervention to increase men's HIV testing uptake, increase their linkage to and uptake of ART and PrEP, and improve their outcomes (virologic suppression for HIV-infected men and adherence to PrEP in uninfected men)			
Study Population:	At least 650 and up to 1,800 men aged ≥18 years who are primarily working in the fishing industry or related activities, who reside in beach communities in Siaya. Study population will consist of up to 140 clusters of men with close social network ties with a variable number of men in each cluster.			
Description of Sites/Facilities Enrolling Participants:	 Clinic sites: up to 10 beach landing sites and associated clinics, within one or more sub-counties, Rarieda, Bondo and Alego Usonga, in Siaya County in western Kenya Community sites: up to 10 Lake Victoria beach communities (with Beach Management Unit -governed landing sites) within sublocations in Rarieda, Bondo and/or Alego Usonga 			

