After the training, the intervention promoters will receive multiple HIV self-test kits for distribution to other men in their close social networks. The HIVST distribution will be as follows: each network-central promoter will receive a test kit for himself, and an addition number of kits (up to 8), for as many of his close network members as identified during the mapping exercise. They also will be given, and asked to distribute to men in their close social networks, transport vouchers for ART or PrEP after HIV self-testing. The voucher worth Ksh 500 (~\$5) will be used for reimbursement when seeking confirmatory testing for HIV and screening for ART or PrEP within 3 months of self-testing at home. The amount reflects prevailing transport and opportunity costs of time. In the session for promoters in the control group, the promoters will be given vouchers with information on facilities with free HIV testing and free self-tests at nearby health facilities, to distribute to men in their close social networks. The control promoters will receive a voucher with information about where to get an HIVST or standard HIV testing within the facilities in the community. The voucher will not have any monetary value. All promoters, in both groups, will be given up to Ksh 1000 (~\$10) for their participation in a full day of training.

Training curriculum is attached to this protocol.

8.6 3-MONTH FOLLOW UP SURVEYS/BASELINE FOR NEW PARTICIPANTS

Up to n=1500 participants

Visit 1 for new participants (those not mapped in the baseline but received self-tests with incentive vouchers (intervention) or referral vouchers (control) from promoters

Visit 3 for baseline mapped and surveyed participants who received self-tests with incentive vouchers (intervention) or referral vouchers (control) from promoters

Visit 4 for promoters who will have participated in the social network survey, baseline survey, and promoter trainings (visits 1 2 and 3, respectively)

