#### 3) Protocol version

This SAP references Owete Protocol Version 4.0, last updated May 5, 2020.

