#### 10) Randomization

The study will take place in Siaya county, which borders Lake Victoria and has a population of ~1 million. Its subcounties, Rarieda, Bondo, and Alego Usonga, have an estimated 79 beaches and nearly 38,000 fisherfolk. Its population relies heavily on fishing and subsistence farming, and has high rates of poverty. Siaya County is also burdened by high rates of HIV, tuberculosis and malaria. HIV prevalence is 19.5%, 28.9% in those aged 25-49 years, and highest among fisherfolk at 32.1%. High-risk behaviors, including concurrent partnerships, the "jaboya" sex-for-fish economy, and low condom use, enhance HIV risks.

To implement this study, trained RAs will conduct a census of selected beach communities in Siaya. In addition to the census, we will rely on the BMU registries to account for the

possibility that the census omits some fishermen. Using the social network data obtained from the census along with a name matching algorithm, we will identify close male social networks that exist in study communities. " close "networks will typically include 4-10 men. Their defining characteristic will be that individual members of any given network will be connected to each other on multiple domains that indicate strong ties between them. Following the identification of distinct close social networks in communities, we will analyze the network data to determine a *network-central man* having a high degree of connectedness across domains within each network. This man will be considered as the network-central 'promoter' of HIV testing and will be the main individual study staff will contact to implement intervention and control group activities and approached for consent. If a central man is not interested in participation, we will approach the next most central man. Local close networks with consenting promoters will be eligible for randomization.

Close social networks will be randomized 1:1 to intervention and control arms using a computer algorithm that performs randomization stratified by beach and network size in 8 blocks of 2 networks. All network members will receive the study arm condition to which their network is assigned. Participation of all network members is not a requirement for network randomization.

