### 19) Adherence and protocol deviations:

- a. Definition of exposure to the intervention and how this is assessed including extent of exposure:
  - ii. Exposure to the intervention will be measured in two independent parts:
    - 1. Being randomized to the intervention or control group. An individual's cluster will be randomized to either intervention or control group if they are part of a social network or designated as the promotor, or
    - 2. Receipt of the intervention (self-testing kit) from the social network promotor.
- b. Description of how adherence to the intervention will be presented consort diagram and brief description in the narrative

iii. Adherence to the intervention will be measured in the following ways:

	Table 1. Owele 5	tudy Huchty Wiedsur	CJ	
Intervention Component	Corresponding Study Aim	Fidelity Measure	Components	Time
Promotors training	Aim 1	Pre- and post- evaluation	Covers self- evaluation of knowledge of HIVST, confidentiality, and the roles of promotors	At beginning and end of promotor training
Promotors training	Aim 1	Pre- and post- evaluation	Promotor training attendance—sign in sheet	At training
Distribution of HIVST	Aim 2	Record of distribution by FRAs	Documentation of kits distributed by RAs to promotors which includes serial #s, expiry date, & distribution date.	At kit distribution date which should be last day of training.
Distribution of HIVST	Aim 2	Record of distribution by promotors	Self-reported list of fishermen the promotors gave kits to.	Collected by FRAs after all kits have been distributed during promotor follow up visit?
Receipt of HIVST	Aim 2	Record of receipt of HIVST from promotor	In 3 month survey. Need to add to survey to ask for name of promotor	During 3 month follow up
Usage of HIVST	Aim 2	Record of use of HIVST	In 3 month survey, will ask about use since baseline	During 3 month follow up
Engagement in Care	Aim 3	Linkage register – blue/green card extraction	Record (to validate self-reported clinic attendance)	During follow up visits
Receipt of HIVST, Engagement in Care	Aim 2-3	Receipt of transport voucher with unique ID	Transport voucher with unique network ID to give to clinic staff.	Attending confirmatory test visit

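### The cap of nine self-test kits per intervention promoter leaves at least one man in a 10-man network without a kit, contrary to protocol 6.5 (minor)

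*Protocol*

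**What the plan says.** Protocol 6.5 randomises close social networks 1:1, stratified by beach and network size, and states that "All network members will receive the study arm condition to which their network is assigned". It adds that a network can be randomised without every member taking part.

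Protocol 8.5 sets the kit supply in the intervention arm: "each network-central promoter will receive a test kit for himself", plus "an addition number of kits (up to 8), for as many of his close network members as identified during the mapping exercise". The same paragraph has the promoter hand out transport vouchers, with no stated ceiling. Control promoters hand out facility vouchers, also with no stated ceiling.

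On network size, SAP section 10 says that "networks will typically include 4-10 men". The protocol synopsis refers only to up to "140 clusters of men with close social network ties with a variable number of men in each cluster", and protocol 1.2 uses an average of 7. Neither document states a maximum.

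SAP section 19 lists, as one of two measures of exposure, "Receipt of the intervention (self-testing kit) from the social network promotor". SAP section 20.a keeps everyone randomised in the intent-to-treat set, whether or not he received a kit.

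**The concern.** Nine kits cannot cover ten men, and ten lies inside the range that the SAP calls typical. Section 8.5 is also strained on its own terms: a fixed ceiling and a supply matched to the mapped members agree only if no network has more than eight members besides the promoter, and the protocol nowhere says so.

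The shortfall can arise only in the intervention arm, because control promoters hold vouchers rather than kits. A man left without a kit is still counted as an intervention man, which pulls the Aim 1 difference toward zero.

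Aim 2 may be touched as well. SAP section 9 has transport vouchers given out when self-tests are distributed, and protocol Table 5 ties redemption to having used a self-test. A man without a kit may therefore miss the linkage incentive.

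There is also no slack at nine men. Protocol 9.1 and 9.2 expect that some promoters may give kits to men outside the network.

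**Working it through.** **Kit count.** Kits per intervention network = 1 + 8 = 9 (protocol 8.5).

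- If the SAP's 4–10 men include the promoter, networks of 4 to 9 are covered and a network of 10 is 10 − 9 = 1 kit short.
- If 4–10 excludes the promoter, 9 others (10 men) are 1 kit short and 10 others (11 men) are 2 kits short.

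**The plan's own power figure.** Inputs from protocol 1.2: 38% against 52%, ICC 0.15, 70 clusters per arm, mean size 7, type I error 5%. Two-sided testing is from SAP 16.

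- Design effect = 1 + (7 − 1) × 0.15 = 1.90.
- Effective n per arm = 70 × 7 / 1.90 = 257.9.
- Power = Φ[(d − 1.96·√(2p̄(1 − p̄)/n)) / √((p₁(1 − p₁) + p₂(1 − p₂))/n)]. With d = 0.14 and p̄ = 0.45 this is Φ[(0.14 − 0.0859)/0.0434] = Φ(1.25) = 89.4%.

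This agrees with the stated 80% or greater.

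**Dilution.** Let f be the share of intervention men without a kit, and assume that such a man tests at the control rate. The intervention proportion becomes 0.38 + 0.14 × (1 − f). Within one 10-man network that is one man short, the 14-point effect becomes 14 × 0.9 = 12.6 points.

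The documents give no distribution of network sizes, so those below are assumptions.

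| Assumed sizes | f | Intervention proportion | Power |
|---|---|---|---|
| No shortfall, mean 7 | 0 | 52.0% | 89.4% |
| 4–10 equally common, promoter included (mean 7) | 1/49 = 2.0% | 51.7% | 88.2% |
| 4–10 equally common, promoter excluded (totals 5–11, mean 8) | 3/56 = 5.4% | 51.3% | 87.8% |
| Half of networks 4 men, half 10 (mean 7, promoter included) | 1/14 = 7.1% | 51.0% | 84.6% |

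The third row uses its own mean of 8: design effect 1 + 7 × 0.15 = 2.05, effective n = 560/2.05 = 273.2, and 91.0% without a shortfall. Holding the mean at 7 with the same f would give 85.9%.

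**Unequal sizes.** The table uses the plan's equal-size design effect. With 1 + ((CV² + 1)m − 1) × ICC instead, power without and with the shortfall is:

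- second row (CV 2/7, design effect 1.99): 88.1% and 86.7%;
- third row (CV 2/8, design effect 2.13): 90.0% and 86.6%;
- fourth row (CV 3/7, design effect 2.09): 86.3% and 81.0%.

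The part due to the kit cap is 1 to 5 points, and power stays above 80% in each case.

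**Kits needed to close the gap, 70 intervention networks.** Second row: 70 × 1/7 = 10. Third row: 70 × 3/7 = 30, or about 26 if the arm is held at 490 men (490 × 0.0536). Fourth row: 70 × 1/2 = 35.

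**The case against.** The strongest reply is that the two figures come from different designs. The SAP says "This SAP references Owete Protocol Version 4.0, last updated May 5, 2020", whereas the kit cap is in protocol version 11.0. Between them the plan moved from 40 clusters per arm of average size 8 to 70 per arm of average size 7. The 4–10 range is descriptive rather than a limit, and eight may simply be the largest number of members expected per promoter. This stands as an account of how the mismatch may have arisen. It does not remove the mismatch: the SAP supplied is the one in force, and if eight is meant as a limit on members, the protocol should say so where networks are formed.

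Other replies stand and limit the point.

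- A man without a kit is not wholly untreated. He still has a trained promoter who encourages and informs him.
- Not every member need take part, so some shortfalls would not bite.
- SAP section 19 records kits issued, recipients and receipt, so a shortfall would be seen.

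Several stronger readings are tempting, and the documents do not support them.

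- A reader might infer that men in large networks generally go without kits. The shortfall is one man, or two, in a network at the top of the range.
- A reader might infer that keeping these men in the intent-to-treat set is a fault. It is correct practice; the fault lies in the supply rule.
- A reader might infer that transport vouchers are capped too. No cap is stated, and a shortage follows only if vouchers are given strictly with kits.
- A reader might infer that the cap would distort a planned analysis of effect by network size. Protocol 1.3.2 lists size as a predictor of testing, no arm-by-size interaction is specified, and SAP 27.g plans no subgroup analyses.

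**Conclusion.** The conflict is real and minor. The kit cap in protocol 8.5 and the size range in SAP 10 cannot both stand with the rule in protocol 6.5, because a 10-man intervention network is at least one kit short.

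The consequence is a small bias toward no difference, in one arm only: about 2% to 7% of intervention men under the assumed size distributions. With the plan's equal-size design effect, Aim 1 power is about 85–88% against 89.4% without a shortfall. It would be wrong to infer that the planned power is lost.

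This rests on three assumptions: the size distributions, which the documents do not give; testing at the control rate by a man without a kit, which overstates the harm if promoter contact alone has some effect; and the protocol's 70 clusters per arm. The SAP's 40 clusters of 8 give 70.2% before any dilution. That is a separate matter which the kit cap does not cause. A network larger than 10, or kits passed outside the network, would widen the gap.

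**What to change.** Reconcile protocol 8.5, protocol 6.4/6.5 and SAP 10 in one of two ways, according to what was intended.

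- **Supply follows the mapping.** Delete the numeric ceiling in 8.5 and state that each intervention promoter receives a kit for himself, and kits and transport vouchers equal in number to the other mapped members of his network.
- **Size is limited.** If eight is the largest intended number of members besides the promoter, state in 6.4/6.5 a maximum network size of nine including the promoter, applied before randomisation in both arms, and change the range in SAP 10 to match.

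In either case, say in SAP 10 whether the stated size counts the promoter.

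The second route costs wording only. The first adds roughly 10 to 35 kits across the trial under the assumed distributions. At the $2 per test given in protocol 4.2 that is about $20 to $70, apart from any extra vouchers.
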